### **10.3. Subject Status and Classification (please refer to Figure 2 for a summary)**

#### **Consent Ineligible**

A subject who has signed informed consent but is found to not meet eligibility criteria will be classified as “**Consent Ineligible**”. There are no FU or adverse event reporting requirements for consent ineligible subjects. Subjects determined to be Consent Ineligible according to statements above do not count towards the enrolment ceiling and will not be used for analysis of the endpoints. The original signed Informed Consent must be maintained in the center’s administrative file.

### **Intent**

A subject who signs informed consent, meets eligibility criteria, but then does not undergo an implant of a WATCHMAN device will be classified as “**Intent**”. This definition includes subjects that do not meet echocardiographic criteria for a WATCHMAN implant at the implant TEE/CT evaluation (e.g. a thrombus has developed in the LAA, inappropriate LAA size). These patients may be withdrawn immediately, unless re-assessment of the criteria is planned.

Subjects who have been consented, but not yet implanted at the time of enrolment closure will also be classified as **Intent**. There are no FU or adverse event reporting requirements for Intent subjects. Intent subjects do not count towards the enrolment ceiling and will not be used for analysis of the endpoints. The original signed Informed Consent must be maintained in the center’s patient file. For these subjects, the eCRFs in the “Baseline” folder and a “Patient Status” form must be completed. Subjects who become Intents due to death before the implant procedure must have the death documented.

### **Attempt**

A subject who signs informed consent, meets eligibility criteria and has had the WATCHMAN Access Sheath inserted to implant the device, but eventually does not receive a WATCHMAN device will be classified as “**Attempt**”. These subjects may be withdrawn, unless a re-implant of a study device is planned, per physician discretion. These subjects will be handled as “Implant” (see next section), if the re-implant is successful. Subjects who eventually have not received a WATCHMAN device at the time of enrolment closure will remain classified as “Attempt” and be withdrawn. There are no FU requirements for Attempt subjects; however, adverse events will be collected up to the point of subject withdrawal. Attempt subjects count towards the enrolment ceiling and will be used for analyses of the endpoints. The original signed Informed Consent must be maintained in the center’s study file and the following forms must be completed:

- eCRFs in the “Baseline” and “Implant” folders
- “Adverse Event” forms for any adverse event that occurs after signing the Informed Consent, up to the point of subject withdrawal.
- “Patient Status” form for withdrawal, when applicable.

[figure not shown]
The date at which the patient status form has been completed will be the point of subject withdrawal.

### **Implant**

A subject who is successfully implanted with the WATCHMAN device will be classified as “**Implant**”. These subjects are followed in accordance with the FU schedule and

included in all study analyses. All applicable case report forms per the protocol must be completed. The original signed Informed Consent and any relevant documentation must be maintained in the center's patient file.

Figure 2: Subject Status and Data Collection Flow Chart

## 11. Study Methods

### 11.1. Data Collection

To ensure data quality and completeness, all required data will be recorded on case report forms (CRFs) provided by the sponsor. Data will be entered onto electronic case report forms by the investigational site or designee. Case Report Forms should be completed accurately during and in a timely manner after any visit in the study. The Principal Investigator or appointed designee must review the case report forms and sign them, certifying their accuracy. Completed case report forms should be submitted to the sponsor within two weeks of completion of a study visit.

Each patient will be followed for a period of two years after implant according to the schedule and standard practice at the enrolling centers. There will be no additional visits, nor procedures, for subjects who participate in the study. Subjects are expected to be followed at implant, then at one post-implant visit (typically between 1-3 months of implant), and then annually through 2 years post implant. An intermediate visit may be a scheduled in a number of patients, per physician discretion. In order to reliably capture

patient status at study end a FU window of  $24 \pm 3$  months will be considered acceptable for scheduling the last visit.

For subjects who are not scheduled to visit the clinic for a follow-up, a subject contact (e.g. phone call) will ensure capture of the endpoint related information, however it is recommended to perform an in-office visit for at least the first annual visit.

**Table 2** provides an overview of the data to be collected at each visit.

**Table 2: Data Collection Overview**

Data Collected	BASELINE	IMPLANT	Follow Up		
			Post-implant Visit*	FU office visit	FU phone visit
Informed Consent	X				
Inclusion/Exclusion	X				
Demographic data	X				
Medical History	X				
LAA imaging (e.g. TEE)		X	X §	X **	
Medication Regimen	X	X	X	X	X
Current status and Vital Signs	X	X	X	X	
Adverse Event Reporting	X	X	X	X	X

\*expected 1-3 month from implant depending on center's practice

§ Control TEE/CT is clinical standard after the Watchman procedure to ensure sealing and exclude thrombus on the device prior to stop dual platelet inhibition or warfarin

\*\* collected only if performed, according to center's practice

### 11.2. Informed Consent

In order to determine eligibility of a subject, the investigator needs to implement the consent process and verify and document the subject meets the inclusion/exclusion criteria. Informed consent is required from all patients (or their legal representatives) prior to the patient's participation in the study. The patient should be given ample time to consider participation and ask questions if necessary. An approved informed consent form shall be signed and personally dated by the subject (or legal representative). The original, signed document is to be kept with the subject's file and a copy must be provided to the subject.

### 11.3. Study Candidate Baseline

Only those subjects who provide consent and meet all of the study enrolment criteria may be enrolled and will have Baseline data collected. Subjects who provide informed

consent but do not meet all of the study enrolment criteria will be considered Consent Ineligible.

The data collection at Baseline includes:

- Demographic data, including: age at time of consent, gender;
- Risk factors, including those used to calculate HAS-BLED, CHADS2 and CHA2DS2-VASc scores;
- Medical and cardiac history, including: cardiovascular diseases; prior history of ischemic stroke, hemorrhagic stroke or TIA; previous cardiac procedures; history of bleeding; indication for LAA occlusion;
- Current medical status; vital signs; AF status (paroxysmal, persistent, permanent);
- Current medication regimen for the use of antiplatelet and anticoagulation medications;
- Adverse Events, if applicable.

#### **11.4. LAA Imaging (e.g. TEE/CT/MRI)**

Prior to implantation with the WATCHMAN device, an implant TEE (or alternative imaging method) is a clinical standard to confirm there is no thrombus in the LAA or left atrium. The implant LAA imaging will also allow the investigator to obtain proper measurements of the LAA to correctly size the device, confirm device release criteria are met prior to device release, and to confirm adverse events have not occurred during the implant procedure (i.e., pericardial effusion). If an intracardiac thrombus is visualized by echocardiographic imaging, the patients will not be implanted. Re-assessment may be scheduled per physician's discretion.

The first control LAA imaging, normally between 1-3 months post-implant, is a clinical standard after the WATCHMAN procedure, it is conducted to assess flow through and around the WATCHMAN device, to ensure sealing and to verify there is no thrombus on the surface of the device prior to stopping dual platelet inhibition or warfarin. Additional LAA imaging may be conducted at the discretion of the investigator and according to center's practice.

Certain information from TEEs conducted during the course of the study will be captured on the study case report forms, including: heart rhythm; valve status; pericardial status; atrial septum characteristics; LAA size and type of anatomy; thrombus assessment.

#### **11.5. Implant Procedure**

The implant procedure should be performed using standard of care methods established by the investigational center (e.g. sterile technique, personnel requirements, etc.). Implantation of the WATCHMAN LAA Closure Device should only be performed by physicians trained in percutaneous and transseptal procedures who have completed the WATCHMAN training program. Refer to the WATCHMAN LAA Closure Technology

Directions for Use for detailed instructions regarding the implantation and use of the WATCHMAN technology. The following will be assessed during implant procedure and documented on case report forms for enrolled subjects:

- WATCHMAN Device and Access System usage information, including device size and compression post-implant;
- LAA imaging (as described in section 11.4): LAA measurements; intracardiac thrombus, device position, LAA seal, thrombus on the device surface;
- Concomitant procedures;
- Current medical status; vital signs; AF status;
- Current medication regimen for the use of antiplatelet and anticoagulation medications;
- Serious adverse events and adverse events during implant procedure. Data to be collected for peri-procedural complications include, but are not limited to:
  - Cardiovascular events: pericardial effusion, cardiac tamponade, bleeding, stroke (ischemic/non-ischemic), TIA, systemic embolism (please refer to Appendix A for definitions of stroke/TIA and classification of bleeding events)
  - ICU : Length of stay
  - Conventional care unit: Length of stay
  - Device/procedure related complications

#### **11.6. Follow-up Procedures**

Subjects are expected to be followed at one post-implant visit (typically between 1-3 months of implant), and then annually through 2 years post implant or until the study is terminated. An intermediate visit may be scheduled in a number of patients, per physician discretion. In order to reliably capture patient status at study end a FU window of  $24 \pm 3$  months will be considered acceptable for scheduling the last visit. For subjects who are not scheduled to visit the clinic for a follow-up, a subject contact (e.g. phone call) will ensure capture of the endpoint related information, however it is recommended to perform an office visit for at least the first annual visit.

##### **i) In-Hospital Visit**

The following will be assessed during each in-hospital visit and documented on case report forms for enrolled subjects:

- Current medication regimen for the use of antiplatelet and anticoagulation medications;
- Procedures performed since last visit;

- Current medical status; vital signs; AF status;
- LAA imaging (as described in section 11.4): device position, LAA seal, thrombus on the device surface, intracardiac thrombus and residual atrial septal shunt;
- Serious adverse events and adverse events experienced since last visit. Data to be collected include, but are not limited to (please refer to Appendix A for definitions of stroke/TIA and classification of bleeding events):
  - ER admission due to WATCHMAN implant related clinical events (stroke/TIA (ischemic/non-ischemic), systemic embolism, major and minor bleeding)
  - Hospitalization (ICU and Ward) due to WATCHMAN implant related clinical events (stroke/TIA (ischemic/non-ischemic), systemic embolism, major and minor bleeding)
  - Specialist visits due to WATCHMAN implant related clinical events (stroke/TIA (ischemic/non-ischemic), systemic embolism, major and minor bleeding)
  - Diagnostic procedure following a clinical event related to WATCHMAN (stroke/TIA (ischemic/non-ischemic), systemic embolism, major and minor bleeding)

## ii) Subject Contact

For subjects who are not scheduled to visit the clinic for a follow-up, a subject contact (e.g. phone call) will ensure capture of the endpoint related information. The following will be assessed during each subject contact and documented on case report forms for enrolled subjects:

- Current medication regimen for the use of antiplatelet and anticoagulation medications
- Serious adverse events and adverse events experienced since last visit. Data to be collected include, but are not limited to (please refer to Appendix A for definitions of stroke/TIA and classification of bleeding events):
  - ER admission due to WATCHMAN implant related clinical events (stroke/TIA (ischemic/non-ischemic), systemic embolism, major and minor bleeding)
  - Hospitalization (ICU and Ward) due to WATCHMAN implant related clinical events (stroke/TIA (ischemic/non-ischemic), systemic embolism, major and minor bleeding)
  - Specialist visits due to WATCHMAN implant related clinical events (stroke/TIA (ischemic/non-ischemic), systemic embolism, major and minor bleeding)

- Diagnostic procedure following a clinical event related to WATCHMAN (stroke/TIA (ischemic/non-ischemic), systemic embolism, major and minor bleeding)

### 11.7. Study Completion

Each subject will be followed for 2 years after the implant. In order to reliably capture subject status at study end, FU assessment at  $24 \pm 3$  months following implant will be considered acceptable. In case of premature termination of the study, data collection will stop accordingly. As this is an observational study, subjects will be managed according to standard of care as per centers practice following termination/completion of the study.

### 11.8. Source Documents

Printed, optical or electronic document containing source data shall be used; examples include hospital records, laboratory notes, device accountability records, radiographs, records kept at the investigation site, and at the laboratories involved in the clinical study.

Where copies of the original source document as well as printouts of original electronic source documents are retained, these shall be signed and dated by a member of the investigation center team with a statement that it is a true reproduction of the original source document.

## 12. Statistical Considerations

An overview of the study design, sample size and statistical analysis is provided below.

### 12.1. Sample Size Justification

This is a prospective, multi-center non-randomized observational study with no formal pre-specified hypothesis test. All subjects will be followed for up to 2 years or until the study is terminated.

A sample size of up to 1000 subjects was chosen to assess incidence of rare events with a large degree of precision. **Table 3** provides the two-sided 95% confidence interval width assuming an event rate of 5%.

**Table 3: Two-Sided Confidence Interval by Sample Size**

Sample Size	95% CI
500	5% $\pm$ 1.9%
750	5% $\pm$ 1.6%
1000	5% $\pm$ 1.4%

### 12.2. Statistical Analysis

Analysis will include all subjects enrolled into the study who undergo an attempted implant of the WATCHMAN device. While no formal hypothesis tests will be performed, descriptive statistics will be generated for the data collected at baseline, during the implant procedure and at follow-up. For continuous variables, the mean, standard deviation, median, range and 95% confidence intervals will be reported. Confidence intervals (95%) for the difference between means will be used to compare groups. For proportions, 95% confidence intervals will be reported. For time-to-event analyses, all subjects not having an event or lost to follow-up will be censored at the time of the last documented follow-up visit. Analyses may include, but will not be limited to, the following: procedural success, procedural complications, and incidence stroke/TIA.

A variety of methods may be utilized in order to assess associations between the likelihood of each of the three outcomes and the patient and procedural characteristics outlined below. Covariates will be chosen for inclusion in the models based on the number of patients with complete data for each outcome according to the prioritization in Table 4: Covariates of Interest.

Methods to model multivariate associations may include but are not limited to the following:

- Univariate analysis of individual predictors, and subsequent construction of multivariate logistic regression models incorporating all significant univariate predictors.
- Parsimonious multivariate logistic regression models constructed through stepwise selection algorithm.
- Classification and regression tree models.

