Key Inclusion Criteria	
A subject may be enrolled in the study if all of the following inclusion criteria are met, provided no exclusion criteria are met:
 
 
1. Patients who are eligible for a WATCHMAN device according to current international and local guidelines (and future revisions) and per physician discretion;
 
2. Patients who are willing and capable of providing informed consent, participating in all testing associated with this clinical investigation at an approved clinical investigational center;
 
3. Patients whose age is 18 years or above, or of legal age to give informed consent specific to state and national law.
 
					
Key Exclusion Criteria	
Subjects will be excluded from the study if they meet any of the following criteria:
 
 
1. Patients who are currently enrolled in another investigational study or registry that would directly interfere with the current study, except when the patient is participating in a mandatory governmental registry, or a purely observational registry with no associated treatments. Each instance should be brought to the attention of the sponsor to determine eligibility.
 
2. Women of childbearing potential who are, or plan to become, pregnant during the time of the study (method of assessment upon physician's discretion);
 
					

EWOLUTION - REgistry on WATCHMAN Outcomes in Real-Life Utilization									
	3. The subject is unable or not willing to complete follow-up visits and examination for the duration of the study.								
Statistical Methods									
Statistical Test Method	No formal pre-specified hypotheses will be tested. However, a variety of statistical modeling methods may be utilized in order to assess associations between the likelihood of each of the three outcomes and the pre-specified patient and procedural characteristics, including multivariate logistic regression and classification and regression tree models.								

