**Table 1: Clinical Studies of the WATCHMAN Device**

Study	Dates of Enrolment	Enrolled Subjects	Sites	Follow-Up
Pilot (feasibility study)	Aug 2002 – Jan 2005	66	8	U.S. subjects completed 5 years; OUS subjects completed up to 9 years.
PROTECT AF (pivotal study)	Feb 2005 – Jun 2008	800	59	Ongoing through 5 years
CAP Registry	Aug 2008 – Jun 2010	566	26	Ongoing through 5 years
ASAP (feasibility study)	Jan 2009 – Nov 2011	150	4	Ongoing through 2 years
PREVAIL (pivotal study)	Nov 2010 – Jun 2012	461	41	Ongoing through 5 years
CAP2 Registry	Sep 2012 - ongoing	Up to 1500	Up to 60	Ongoing through 5 years

The first pilot study demonstrated that the WATCHMAN device was safe and met the performance criteria for use in subjects with non-valvular atrial fibrillation.

The first pivotal study, WATCHMAN Left Atrial Appendage System for Embolic PROTECTION in Patients with Atrial Fibrillation (PROTECT-AF), demonstrated non-

inferiority of the WATCHMAN device to long-term warfarin therapy for the primary efficacy endpoint of stroke, systemic embolism and cardiovascular death.

Most recent data analysis of The PROTECT AF trial has shown that the WATCHMAN device achieved superiority for the combined endpoint of all stroke, cardiovascular or unexplained death and systemic embolism (for Bayesian analysis, posterior probabilities are used to determine superiority; > 95% represents superiority).

- The observed primary efficacy event rate was 2.3 percent and 3.8 percent in the WATCHMAN and control groups, respectively, demonstrating a 40 percent relative risk (RR) reduction in primary efficacy in the WATCHMAN group (RR = 0.60, posterior probability of superiority = 96 percent).

Secondary analysis also showed a relative risk reduction and superiority to control for all-cause mortality and cardiovascular mortality.

- All-Cause Mortality: the WATCHMAN group was superior to the control group, 3.2 percent to 4.8 percent respectively, representing a 34 percent relative risk reduction in all-cause mortality in the WATCHMAN group (Hazard ratios [HR] = 0.66, p=0.0379).
- Cardiovascular Mortality: the WATCHMAN group was superior to the control group, 1.0 percent and 2.4 percent respectively, representing a 60 percent relative risk reduction in cardiovascular death in the WATCHMAN group (HR = 0.40, p=0.0045).

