The Continued Access to PROTECT Registry (CAP Registry) provided continued access of the WATCHMAN device to PROTECT-AF investigators and demonstrated a decrease in procedural complications of pericardial effusion with tamponade, cardiac perforation and device embolization (1.2%, 0.2%, 0%, respectively).

The second pivotal study, Prospective Randomized Evaluation of the WATCHMAN LAA Closure Device In Patients with Atrial Fibrillation Versus Long Term Warfarin Therapy (PREVAIL), was conducted to provide additional information on the implant procedure and complication rates associated with the device.

The ASA Plavix Feasibility Study With WATCHMAN Left Atrial Appendage Closure Technology (ASAP) study was a feasibility study conducted in Europe to characterize the performance of the WATCHMAN device in non-valvular atrial fibrillation (AF) subjects with contraindications to warfarin therapy.

The Continued Access Protocol (CAP2) is a prospective, non-randomized, multicenter study to allow continued access to the WATCHMAN LAA Closure Technology during the data analysis, reporting and review of the PREVAIL pivotal study Pre-Market Application by FDA.

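### The optional predictor models in section 12.2 keep covariates by significance; if only the kept ones are reported, a modest true association will be overstated (minor; wording change only)

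*Combined protocol and SAP*

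**What the plan says.** Section 12.2 plans descriptive statistics with 95% intervals and no formal hypothesis tests. It then allows models relating three outcomes (it has just listed procedural success, procedural complications and stroke/TIA) to patient and procedural characteristics. The first method is "Univariate analysis of individual predictors, and subsequent construction of multivariate logistic regression models incorporating all significant univariate predictors". The second is "Parsimonious multivariate logistic regression models constructed through stepwise selection algorithm". The third is classification and regression trees. The list is open-ended, and the synopsis is equally permissive: "a variety of statistical modeling methods may be utilized in order to assess associations".

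The candidates come from Table 4: ten covariates, with age, HAS-BLED, CHADS2 and CHA2DS2-VASc each given only as a single cut-point. Priority among them follows the Table 4 order and data availability: "Covariates will be chosen for inclusion in the models based on the number of patients with complete data for each outcome". That rule deals with incomplete data. It does not replace the significance step.

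The plan gives no significance level, stepwise criterion, shrinkage or validation, and no rule on whether covariates that are not kept will be reported.

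**The concern.** A covariate that is kept because its estimate is far enough from the null has, on average, an estimate further out than the truth. The weaker the true association and the fewer the events, the stronger this effect. The sample size was chosen for precision on rare events, so few events are to be expected.

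These are the only association methods that the plan names. The publication policy (section 23) commits the sponsor to submitting results and encourages sub-analyses, and section 6 says that the data may be needed for reimbursement. A risk factor with a modest true effect could therefore be published with too large an odds ratio and an interval that covers too rarely.

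**Working it through.** **Inputs from the documents.** Sample size up to 1000 and event rate 5% (section 12.1). Ten candidates in Table 4: eight two-level and two three-level, so 8 × 1 + 2 × 2 = 12 parameters. The introduction (section 4, clinical study experience) supplies lower rates for comparison: "The observed primary efficacy event rate was 2.3 percent and 3.8 percent in the WATCHMAN and control groups", and procedural complications of "pericardial effusion with tamponade, cardiac perforation and device embolization (1.2%, 0.2%, 0%, respectively".

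**Assumptions, not in the documents.** Selection at p<0.05, covariate prevalence 25%, true odds ratio 1.5 (2.0 also tried), independent covariates, and the 100-event scenario.

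**1. The plan's own figure.** Half-width = 1.96 × √(0.05 × 0.95 / n) gives 1.91%, 1.56% and 1.35% for n = 500, 750 and 1000. Table 3 states 1.9%, 1.6% and 1.4%, so it reproduces.

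**2. Event counts per 1000.** 5% gives 50. 2.3% gives 23, or 46 if that rate is yearly over two years (the time base is not stated). 1.2% + 0.2% + 0% gives 14 for the three named complications.

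**3. Selection at 50 events, normal approximation.** With 250 patients exposed, 750 unexposed, 50 events and odds ratio 1.5, the expected cells are 16.4 and 233.6 (exposed, with and without the event) and 33.6 and 716.4 (unexposed).

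- SE of the log odds ratio = √(1/16.4 + 1/233.6 + 1/33.6 + 1/716.4) = 0.310.
- Smallest harmful estimate that passes = exp(1.96 × 0.310) = 1.84, already above the true 1.5.
- With log(1.5)/SE = 0.405/0.310 = 1.306, the chance of passing is [1 − Φ(0.654)] + Φ(−3.266) = 25.66% + 0.05% = 25.7%.
- Mean log odds ratio if kept = 0.405 + 0.310 × (0.3222 − 0.0019)/0.2572 = 0.792, so an odds ratio of 2.21.
- Coverage if kept = (0.2566 − 0.025)/0.2572 = 90%.

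**4. Simulation of the procedures.** 1000 patients, the 12 candidate parameters, 3000 replicates per setting. Odds ratios are geometric means among kept estimates.

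| Setting | Kept | Odds ratio if kept | 95% interval covers |
|---|---|---|---|
| 50 events, true 1.5, screen p<0.05 | 25.6% | 2.14 | 89.1% |
| same, screen p<0.01 | 9.4% | 2.49 | 70.9% |
| same, screen p<0.10 | 35.8% | 2.01 | 91.4% |
| same, backward stepwise p<0.05 | 27.1% | 2.14 | 89.7% |
| 23 events, true 1.5, screen p<0.05 | 14.3% | 2.65 | 80.2% |
| 23 events, true 1.5, backward p<0.05 | 15.4% | 2.86 | 83.5% |
| 100 events, true 1.5, screen p<0.05 | 41.5% | 1.84 | 95.0% |
| 50 events, true 2.0, screen p<0.05 | 60.8% | 2.41 | 96.0% |

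A separate simulation with 40% prevalence, three true and seven null covariates gave 2.09 for a true 1.5 under both screen and backward selection, against 1.49 with all ten covariates kept. With covariate correlation 0.3 the selected figures were 1.82 (screen) and 2.22 (backward). The direction was the same in every setting tried.

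**5. The alternative.** A fixed Firth model with Table 4 less the three scores (12 − 3 = 9 parameters), every result reported, gave 1.49 with 94.6% coverage at 50 events and 1.48 with 94.6% at 23. If only its significant results are read at 50 events, the exaggeration returns: 2.13 with 89.3% coverage. The gain therefore comes from reporting everything, not from the penalty.

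**6. False flags, all covariates null, 50 events.** At least one: 41.6% at the screen, 35.6% in the final selected model, and 45.6% with 12 unselected intervals (1 − 0.95^12 = 46.0%).

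**7. Cut-points (separate).** For a normal covariate with a linear effect, a cut with a share q above it keeps φ(z)²/[q(1 − q)] of the information: 0.49, 0.58 and 0.64 at q = 20%, 30% and 50%.

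**The case against.** The models only may be used, nothing is formally tested, and the registry's purpose is descriptive. Candidates and cut-points are listed in advance. All of this stands, and it limits the point to a minor one. It does not make the estimates right if the methods are used.

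Part of the harm depends on reporting, which the plan leaves open. Reporting every univariate result would free the univariate estimates from selection. The adjusted estimates would still be selected.

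The sizes rest on assumed prevalence, odds ratio, threshold and independence. That is fair. The direction is robust; the size is not.

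Several stronger readings are tempting and are not supported:

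- *That the registry's incidence rates are biased.* They do not pass through these models.
- *That stepwise selection is by p-value.* Its criterion is not stated. It acts the same way only if it is a p-value or a similar rule.
- *That non-significant results will be withheld.* The plan does not say so.
- *That the cut-points cause the exaggeration, or were searched for in the data.* They are fixed in Table 4. Their possible cost is precision, and only if the effect is graded; for a true step at the cut they lose nothing.
- *That 2.3% is the stroke/TIA rate to expect here.* It belongs to a composite that adds death and embolism and leaves out TIA, so 23 events is an illustration.
- *That this point shows a need for a time-to-event model for stroke/TIA.* That is a different question, and nothing here bears on it.

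**Conclusion.** The concern holds as a minor, cheaply mended weakness, conditional on two things: the optional selection methods are used, and only the kept covariates are reported. At 50 events in 1000, with an assumed 25% prevalence, p<0.05 and a true odds ratio of 1.5, the association is kept about 26% of the time, reported at about 2.1 to 2.2, and covered by its 95% interval about 89 to 90% of the time. With fewer events it is worse. For a true odds ratio of 2.0 at 50 events, or for 1.5 at 100 events, some overstatement remains but coverage is near nominal. Overstatement is a tendency and not certain for every estimate: at a true 2.0, about 78% of kept estimates in the separate simulation exceeded the truth.

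**What to change.** Replace the first two method bullets of section 12.2 with:

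> For each outcome, one multivariable model with covariates fixed in advance from Table 4 is fitted without a univariate significance screen or stepwise step, using Firth or similar penalisation where events are few. Every fitted covariate is reported with its 95% interval whether or not it is significant, together with the number of events and the number of intervals examined. Results of any tree model are labelled exploratory.

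Keep the Table 4 order as the rule when complete data run short. Do not add a minimum number of events per parameter that removes covariates from the bottom of Table 4. At 23 events, for example, a minimum of 5 would leave only age, gender and type of AF (4 parameters, 23/4 = 5.8 each) and so drop previous stroke/TIA from a stroke/TIA model.

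**Cost.** Plan wording and standard software; no new data. Intervals widen when covariates are correlated. The chance of at least one false flag when all covariates are null is slightly higher, about 46% for 12 unselected intervals against 36 to 42% with selection. The text should therefore say that the intervals are not to be read as tests.

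**Optional and separate.** Section 11.3 already collects age and the score components. Age and each score could also be reported as continuous terms, with the scores in separate models because they share components with other covariates. This gains precision only if the effects are roughly linear.
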